## AMENDMENT HISTORY

Amendment 1.0 (Protocol Version 2.0 dated 20Jul2018): The primary reason for Amendment 1.0, Protocol Version 2.0 dated 20Jul2018 was to decrease the number of subjects enrolled in the study which are sufficient to explore the efficacy and safety in this initial Phase 2 study. In addition, a substudy was added to determine the trough levels of ATI-502 in the blood and pharmacodynamic effects at trough.

Amendment 2.0 (Protocol Version 3.0 dated 19Sep2018): The primary reason for Amendment 2.0, Protocol Version 3.0, dated 19SEP2018 was to add additional safety assessments, specifically – clinical laboratory testing (chemistry and hematology) at Visit 5, Visit 7 and Visit 8 and to remove pharmacodynamic testing in a subset of subjects at Visit 2, Visit 4, Visit 6 and Visit 9.

Amendment 3.0 (Protocol Version 4.0 dated 08Nov2018): The primary reason for Amendment 3.0, Protocol Version 4.0, dated 08NOV2018 is to give subjects the option to initiate treatment with ATI-502 Topical Solution, 0.46% to explore if hair regrowth can be maintained or continued following cessation of treatment with ATI-501 Oral Suspension. Eligible subjects will be given the option at Visit 9 to enter an open-label study ATI-502-AA-203.

## AMENDMENT RATIONALE

The purpose of Protocol Version 5.0 dated 09APR2019 (Protocol Amendment 4.0) is to clarify the primary endpoint will be conducted on the ITT population. In addition, other clarifications were made to the statistical methods as detailed in the following table. All previous amendments have been incorporated into the protocol dated 09APR2019.

## MAJOR PROTOCOL CHANGES

Protocol Version	Date	Section	Revisions
Version 5.0	09APR2019	Statistical Methods -Synopsis, -Section 9.4.1	-Specified that the primary analysis would be on the ITT population, using LOCF for missing data and based upon a mixed effect model repeated measures (MMRM). -Clarified: efficacy variable is “percent change from baseline” and not “mean percent change from baseline”.
		Secondary Efficacy Analyses -Synopsis -Section 9.4.2	-Included a secondary sensitivity analysis on the primary endpoint using the PP population. -Added secondary responder efficacy endpoints to be specified in the SAP -Specified that all secondary efficacy endpoints would be analyzed using the ITT population Deleted: Dichotomous variables will be analyzed using Chi-square tests. Ordinal and continuous variables will be analyzed using appropriate Analysis of Variance models.
		Section 9.4	-Deleted the statement that the PP population would be used for all efficacy analyses -Clarified that Hair regrowth is determined based on both percent change from baseline and absolute change from baseline.
		Synopsis, Section 9.5	Dropped the chi-square test for the overall incidence of AE

**SYNOPSIS**

Name of Sponsor/Company: Aclaris Therapeutics, Inc.	
Name of Investigational Product: ATI-501 Oral Suspension	
Name of Active Ingredient: ATI-501	
Title of Study: A Randomized, Double-Blind, Placebo-Controlled Multicenter Study to Evaluate the Safety, Tolerability and Efficacy of ATI-501 Oral Suspension Compared to Placebo in Adult Subjects with Alopecia Areata, Alopecia Universalis or Alopecia Totalis	
Study center(s): Approximately 25 US study centers	
Studied period (years): Estimated date first patient enrolled: June 2018 Estimated date last patient completed: July 2019	Phase of development: 2

Objectives:
 
Primary:
 
 
To evaluate the safety, tolerability and efficacy of ATI-501 Oral Suspension, 400 mg, 600 mg, 800 mg compared to Placebo Oral Suspension in subjects with alopecia areata (AA), alopecia universalis (AU) or alopecia totalis (AT)
 
 
Secondary:
 
 
To evaluate the psychometric performance of the key clinical outcome assessments and questionnaires with respect to reliability, construct-related validity, and sensitivity to change
 
To generate score interpretation estimates for the clinical outcome assessments to guide the definition of responders in pivotal trials
 
To assess the level of ATI-502 in the blood at trough
 
	

Methodology:
 
This Phase 2, multicenter, randomized study will evaluate the safety, tolerability and efficacy of ATI-501 for the treatment of AA, AU, or AT in adult subjects. Subjects will be required to have a clinical diagnosis of stable AA, AU, or AT with 30% to 100% total scalp hair loss for a duration of at least 6 months up to and including 12 years. A total of 80 subjects will be randomized with approximately 40 subjects enrolled with AU or AT. Subjects will be randomized to a 1:1:1:1 ratio:
 
 
ATI-501 Oral Suspension, 400 mg, BID for 24 weeks (6 months)
 
ATI-501 Oral Suspension, 600 mg, BID for 24 weeks (6 months)
 
ATI-501 Oral Suspension, 800 mg, BID for 24 weeks (6 months)
 
Placebo Oral Suspension, BID for 24 weeks (6 months)
 
 
During the screening period, subjects will be assessed for eligibility into the study. Subjects qualifying for protocol treatment based on the outcome of screening procedures will be randomized to take 400 mg, 600 mg, 800 mg or placebo suspension twice-daily within approximately 30 minutes following morning and evening meals for 24 weeks. Assessment of response to treatment will be performed at Week 4, Week 8, Week 12, Week 16, Week 20, Week 24, and post-treatment Week 28.
	

Safety and tolerability will be evaluated at each study visit by assessment of adverse events, clinical laboratory tests, and vital signs, and at select visits, ECGs will be completed.

Subjects who complete study visits through Visit 9 will have the option to roll over into an open-label study ATI-502-AA-203. Subjects who withdraw consent or meet study medication discontinuation criteria (Section 3.4.1.2) on study ATI-501-AUAT-201 will not be eligible for roll-over to study ATI-502-AA-203. Subjects who complete the assessments for Visit 9 and then meet study ATI-502-AA-203 entry criteria and provide written consent will skip post-treatment Visit 10. Subjects who are not eligible for ATI-502-AA-203 or who decline to participate should return for the final Visit 10 assessments.

**Select Sites:**

At approximately six sites, 24 subjects will have additional blood samples taken for pharmacokinetic analyses. Blood samples will be taken at predose at Visit 2 and at trough at Visit 4, Visit 6 and Visit 9 to determine the concentration of ATI-502 in the blood at trough.

**Number of subjects (planned):** Approximately 95 with approximately 45 subjects enrolled with AT or AU.

Male and female subjects, 18 years of age or older, with a clinical diagnosis of stable AA, AU or AT of the scalp, who meet all the inclusion criteria and none of the exclusion criteria, will be eligible to enroll in this study.

**Inclusion Criteria:**

Subjects must meet the following criteria to be eligible for participation in the study:

1. Able to comprehend and willing to sign an Informed Consent Form (ICF).
2. Male or non-pregnant, non-nursing female  $\geq$  18 years old at the time of informed consent.
3. Have a clinical diagnosis of stable AA, AU or AT (Stable is defined as no current areas of spontaneous terminal scalp hair regrowth).
4. Have a Severity of Alopecia Tool (SALT) score of at least 30% to 100% total scalp hair loss determined by the study investigator at Screening (Visit 1) and Baseline (Visit 2).
5. Subjects with 30% to 95% scalp hair loss (based on SALT score) must have an assessment of “no hair” or “a little hair” in the target scalp patch based on both the Clinician and Subject Alopecia Scalp Appearance Assessment (ASAA). The target patch is defined as the most bothersome patchy area of hair loss as identified by the subject (Refer to Section 7.1).
6. Have a duration of the current episode of stable scalp hair loss for a minimum of 6 months and a maximum duration of hair loss of 12 years (inclusive). [Current episode is defined as the period of the current presentation of hair loss (AA, AU or AT)].
7. If the subject is a woman of childbearing potential (WOCBP), she must have:
  - Negative serum pregnancy tests at Screening (Visit 1); and
  - A negative urine pregnancy test at Baseline (Visit 2); and
  - Agree to not be planning a pregnancy during the study duration and use a highly effective method of contraception for the duration of the study and 30 days after the last dose of study medication. (Refer to Section 8.4.2).
8. Be in good general health and free of any known disease state or physical condition which, in the investigator’s opinion, might impair evaluation of the subject or which might expose the subject to an unacceptable risk by study participation.
9. Be willing to maintain the same hair style and hair dyeing throughout the study period. Subjects who shave their scalp must be willing to refrain from shaving their scalp for at least two weeks prior to each study visit, as determined by the investigator based on the ability to assess visible scalp hair growth. Hair trimming outside the treatment areas to maintain the current hair style is permitted.

10. Be willing and able to follow all study instructions and to attend all study visits.
11. Subjects taking hormonal replacement therapies must be on stable doses for 6 months prior to enrollment and remain on a maintenance dose throughout the study.
12. Subjects taking thyroid replacement medication must be on stable doses for 6 months prior to enrollment and remain on a maintenance dose throughout the study.
13. Sexually active male subjects must agree to use a barrier method of contraception with any WOCBP partner(s) from the first dose of study medication to at least 30 days after the last dose of study medication.

**Exclusion Criteria:**

Subjects are excluded from this study if any 1 or more of the following criteria is met:

1. Females who are nursing, pregnant, or planning to become pregnant for the duration of the study and up to 30 days after the last dose of study medication.
2. Diffuse alopecia areata. [Diffuse alopecia areata is defined as the absence of the typical patchy distribution of hair loss (in subjects with  $\leq 95\%$  total scalp hair loss) with hair thinning distributed throughout the scalp.]
3. Concomitant hair loss disorder (by history or physical exam) such as androgenetic alopecia (AGA) or scarring alopecia (e.g., cicatricial alopecia, frontal fibrosing alopecia, etc.). Subjects without a prior known history of AGA or other patterned hair loss disorder who exhibit AGA or other patterned hair loss with regrowth during the study will be allowed to continue in the study.
4. Active skin disease on the scalp (such as psoriasis or seborrheic dermatitis) or a history of skin disease on the scalp that in the opinion of the investigator would interfere with study assessments of efficacy or safety.
5. Active scalp trauma or other condition affecting the scalp that, in the investigator's opinion, may affect the course of AA, AU or AT or interfere with the study conduct or evaluations.
6. The presence of a permanent or difficult to remove hairpiece or wig that will, in the opinion of the investigator, interfere with study assessments if not removed at each visit.
7. History of, or current, severe, progressive or uncontrolled autoimmune, metabolic, hepatic, endocrine, renal, gastrointestinal, pulmonary, cardiovascular, genitourinary, or hematological disease, neurologic or cerebral disorders, or coagulation disorders that, as determined by the Investigator, would preclude participation in and completion of study assessments.
8. History of, current or suspected systemic or cutaneous malignancy and /or lymphoproliferative disease, other than subjects with a history of adequately treated and well healed and completely cleared non-melanoma skin cancers (e.g. basal or squamous cell carcinoma) treated successfully at least 1 year prior to study entry with no evidence of disease.
9. Evidence of active or latent bacterial (including tuberculosis) or viral infections at the time of enrollment, or history of incompletely treated or untreated tuberculosis. Subjects who have completed therapy for latent tuberculosis may participate. Refer to Exclusion Criterion 12 for herpes zoster, herpes simplex, or cytomegalovirus infections.
10. History of serious local infection (e.g., cellulitis, abscess) or systemic infection including but not limited to a history of treated infection (e.g., pneumonia, septicemia) within 3 months prior to Baseline. Subjects on an antibiotic for a nonserious, acute local infection must complete the course prior to enrollment into the study.
11. Positive for HIV, Hepatitis B or C. Subjects with serologic evidence of Hepatitis B vaccination (HepB surface Ab without the presence of Hep B surface Ag) will be allowed to participate.
12. History of recurrent herpes zoster (more than one episode) or disseminated herpes zoster (a single episode) or disseminated herpes simplex (single episode) or cytomegalovirus (CMV)

- that resolved less than 2 months before study enrollment. Subjects with a history of frequent outbreaks of Herpes Simplex Virus (defined as 4 or more outbreaks a year).
13. Clinically significant laboratory abnormalities at screening that, in the opinion of the Investigator, would make the subject a poor candidate for the study. [Subjects with any Screening laboratory values meeting the Study Medication Interruption Criteria found in [Table 2](#) must have repeat lab testing performed with results meeting the minimum criteria for resumption in order to initiate treatment at Baseline (Visit 2)].
  14. Subjects with absolute neutrophil count  $<1,800/\mu\text{L}$ , or platelet count  $<130,000/\mu\text{L}$ .
  15. Subjects who have received any of the following treatments for the timeframes specified below:
    - Disease Modifying Anti-Rheumatic Drugs (DMARDs), Biologics or immunosuppressants, including but not limited to: anakinra, adalimumab, azathioprine, corticosteroids, cyclosporine, etanercept, infliximab, methotrexate, TNF inhibitors, ustekinumab within 1 month or 5 half-lives (whichever is greater) of Baseline (Visit 2).
    - Plaquenil within 2 months of Baseline (Visit 2).
    - JAK inhibitors (oral or topical) within 6 months of Baseline (Visit 2).
    - Intralesional steroids or platelet rich plasma injections in the scalp within 1 month of Baseline (Visit 2).
    - Topical treatments on the scalp with anthralin, bimatoprost, corticosteroids, diphenylprone, diphenylcyclopropenone (DPCP), squaric acid dibutylester (SADBE), minoxidil, pimecrolimus, or tacrolimus within 1 month of Baseline (Visit 2).
    - Phototherapy (narrow band Ultraviolet B [NB UVB] or broadband therapy) within 4 weeks of Baseline (Visit 2).
  16. Participation in an investigational drug or device trial in which administration of an investigational drug or device occurred within 30 days or 5 half-lives (whichever is longer) of Baseline (Visit 2).
  17. Any condition possibly affecting oral drug absorption, e.g., gastrectomy, clinically significant diabetic gastroenteropathy, or certain types of bariatric surgery such as gastric bypass. Procedures such as gastric banding are not exclusionary.
  18. Sensitivity to any of the ingredients in the study medications.
  19. Unwillingness to refrain from weaves, hair extensions, or shaving of the scalp for at least two weeks prior to a study visit, at the discretion of the investigator, based on the ability to assess hair growth.
  20. Screening ECG findings of:
    - QTcF  $>450\text{msec}$  for males or  $>470\text{msec}$  for females (use of the ECG algorithm is acceptable for this purpose)
    - Heart rate  $\leq 45$  or  $\geq 100$  beats/minutes (A subject with a heart rate  $\leq 45$  beats/min may be enrolled if in the opinion of the investigator the heart rate is not clinically significant).
    - Rhythm disturbance other than sinus arrhythmia or ectopic supraventricular rhythm (ectopic atrial rhythm)
    - Conduction disturbance including PR  $>240\text{msec}$ , pre-excitation (delta wave and PR  $<120\text{msec}$ ), second degree or higher AV block
    - Acute or chronic signs of ischemia
    - Left Bundle Branch Block
    - Prior myocardial infarction
  21. Vaccination with a live or attenuated vaccine within 6 weeks prior to Baseline (Visit 2) or planned vaccination with these vaccines at any time during treatment or within 6 weeks following discontinuation of study medication.

22. Participation in an investigational study with ATI-502 Topical Solution.
 
23. Subjects unwilling to have photographs taken for study purposes.


Investigational product, dosage and mode of administration:
 
ATI-501 Oral Suspension, 400 mg, 600 mg, 800 mg or placebo will be taken approximately 30 minutes after morning and evening meal followed by a large glass of water, twice-daily for 24 weeks.

Duration of treatment:
 
All subjects will take 400 mg, 600 mg, 800 mg or placebo oral suspension twice daily for 24 weeks followed by a 4-week post-treatment follow up period.

Reference therapy, dosage and mode of administration:
 
Placebo suspension, twice daily, oral


Criteria for evaluation:
 
Primary Efficacy:
 
 
The primary efficacy endpoint is the mean percent change from Baseline in the Severity of Alopecia Tool (SALT) score at Week 24 (Visit 9).
 
 
Secondary Efficacy:
 
 
Mean percent change from Baseline in the Alopecia Density and Extent Score (ALODEX) score at Week 24.
 
Change from Baseline in the SALT score at Week 24 (Visit 9) with additional analyses at each applicable post-baseline visit where data are available.
 
Change from Baseline in the Alopecia Density and Extent Score (ALODEX) score at Week 24 (Visit 9) with additional analyses at each applicable post-baseline visit where data are available.
 
Proportion of subjects in each treatment arm achieving at least a 50% reduction in ALODEX score at Week 24 (Visit 9) with additional analyses at each applicable post-baseline visit where data are available compared to Baseline.
 
Proportion of subjects in each treatment arm achieving at least a 50% reduction in SALT score at Week 24 (Visit 9) with additional analyses at each applicable post-baseline visit where data are available compared to Baseline.
 
Change from Baseline in the Alopecia Scalp Appearance Assessment (ASAA) (Patient-reported outcome [PRO]) at Week 24 (Visit 9) with additional analyses at each applicable post-baseline visit where data are available.
 
Change from Baseline in the Alopecia Scalp Appearance Assessment (ASAA) (Clinician-reported outcome [ClinRO]) at Week 24 (Visit 9) with additional analyses at each applicable post-baseline visit where data are available.
 
Change from Baseline in the Physician Global Impression of Severity (PhGIS) at Week 24 (Visit 9) with additional analyses at each applicable post-baseline visit where data are available.
 
Change from Baseline in Alopecia Facial Hair Appearance Assessment (AFHA) (Clinician and Subject) at Week 24 (Visit 9) with additional analyses at each applicable post-baseline visit where data are available.
 
Change from Baseline in the Subject Global Impression of Severity (SGIS) at Week 24 (Visit 9) with additional analyses at each applicable post-baseline visit where data are available.
 
Change from Baseline in the subject reported Alopecia Impact Assessment (AIA) at Week 24 (Visit 9) with additional analyses at each applicable post-baseline visit where data are available.
 
Subject Global Impression of Treatment Satisfaction (SGITS) at Week 24 (Visit 9) with additional analyses at each applicable post-baseline visit where data are available.
 
Change from Baseline in the Subject Global Satisfaction with Hair Quality (SGSHQ) at Week 24 (Visit 9) with additional analyses at each applicable post-baseline visit where data are available.
 


- Change in Dermatology Life Quality Index (DLQI) total score between Baseline and Week 24 (Visit 9) with additional analyses at each applicable post-baseline visit where data are available.
- Global Impression of Change (Clinician and Subject) at Week 24 (Visit 9).

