Week		0	2	4	8	12	16	20	24	28
Treatment Day	-30 to 0	1	15	29	57	85	113	141	169	197
Treatment Window(days)	N/A	N/A	± 3	± 3	± 3	± 3	± 3	± 3	± 3	± 3
SALT Score (prior to ALODEX) 	X	X	X	X	X	X	X	X	X	X
ALODEX Score (after SALT) 	X	X	X	X	X	X	X	X	X	X
Vellus and Indeterminate Hair Assessment	X	X	X	X	X	X	X	X	X	X
Photography (complete scalp)		X		X	X	X	X	X	X	
Subject randomization		X								
Subject instructions 		X		X	X	X	X	X	X	
Dispense study medication 		X	X 	X	X	X	X	X		
Collect study medication and assess compliance 		X	X	X	X	X	X	X	X	X
Concomitant therapies		X	X	X	X	X	X	X	X	X
Adverse events		X	X	X	X	X	X	X	X	X
Abbreviations: CR= Clinician Rating; ET= Early termination Visit; SR= Subject Rating										
 Efficacy assessments completed at Visit 3 are to test the reliability of the clinician and patient reported outcome tools.										
 A written, signed ICF must be obtained from each subject prior to performing any study related procedure ( i.e. , prior to performing vital signs, standardized photography, biopsies, clinical laboratory sampling or urine pregnancy tests).										
 A physical exam includes: general appearance, examination of head, eyes, ears, nose and throat, respiratory, cardiovascular, abdominal, neurological, musculoskeletal, extremities, lymphatic and skin assessment (other than AA).										
 Vitals signs include: oral or ear temperature, blood pressure, heart rate, respiration rate (height and weight at Screening only).										
 Clinical laboratory non-fasting sampling includes: CBC, Chemistry with lipids, Urinalysis. Quantiferon Gold, HIV, Hepatitis B and C, TIBC, Serum Iron, Serum Ferritin, T3, free T4, TSH and Serum Pregnancy should be done at screening visit only.										
 At Select sites: A single 4.5 mL sodium citrate vacutainer should be drawn at Visit 2 (predose) and Visits 4, 6, and 9, 12 hours (± 30 minutes) after the prior evening dose. Subjects participating in the PK analysis should be called the day prior to Visit 4, 6, and 9 to remind them to take their evening dose approximately 11 hours prior to the visit time and to document the time of the evening dose.										

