9. Evidence of active or latent bacterial (including tuberculosis) or viral infections at the time of enrollment, or history of incompletely treated or untreated tuberculosis. Subjects who have completed therapy for latent tuberculosis may participate. Refer to Exclusion Criterion 12 for herpes zoster, herpes simplex, or cytomegalovirus infections.
10. History of serious local infection (*e.g.*, cellulitis, abscess) or systemic infection including but not limited to a history of treated infection (*e.g.*, pneumonia, septicemia) within 3 months prior to Baseline. Subjects on an antibiotic for a nonserious, acute local infection must complete the course prior to enrollment into the study.
11. Positive for HIV, Hepatitis B or C. Subjects with serologic evidence of Hepatitis B vaccination (HepB surface Ab without the presence of Hep B surface Ag) will be allowed to participate.

12. History of recurrent herpes zoster (more than one episode) or disseminated herpes zoster (a single episode) or disseminated herpes simplex (single episode) or cytomegalovirus (CMV) that resolved less than 2 months before study enrollment. Subjects with a history of frequent outbreaks of Herpes Simplex Virus (defined as 4 or more outbreaks a year).
13. Clinically significant laboratory abnormalities at screening that, in the opinion of the Investigator, would make the subject a poor candidate for the study. [Subjects with any Screening laboratory values meeting the Study Medication Interruption Criteria found in [Table 2](#) must have repeat lab testing performed with results meeting the minimum criteria for resumption in order to initiate treatment at Baseline (Visit 2)].
14. Subjects with absolute neutrophil count  $<1,800/\mu\text{L}$ , or platelet count  $<130,000/\mu\text{L}$ .
15. Subjects who have received any of the following treatments for the timeframes specified below:
  - Disease Modifying Anti-Rheumatic Drugs (DMARDs), Biologics or immunosuppressants, including but not limited to: anakinra, adalimumab, azathioprine, corticosteroids, cyclosporine, etanercept, infliximab, methotrexate, TNF inhibitors, ustekinumab within 1 month or 5 half-lives (whichever is greater) of Baseline (Visit 2).
  - Plaquenil within 2 months of Baseline (Visit 2).
  - JAK inhibitors (oral or topical) within 6 months of Baseline (Visit 2).
  - Intralesional steroids or platelet rich plasma injections in the scalp within 1 month of Baseline (Visit 2).

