#### **8.1.1. Demographic/Medical History/ Alopecia Areata History**

During the screening visit, the investigator or designee will interview each subject to obtain demographic information including date of birth, sex at birth, Fitzpatrick skin type, race and, if appropriate, ethnicity. The investigator or designee will interview each subject to obtain medical history information related to all medical conditions, surgeries and disease states that, at screening: are ongoing, require concomitant therapy or are, in the opinion of the investigator, relevant to the subject's study participation. In addition, the medical history of women who are not of childbearing potential should reflect the reason e.g. post-menopausal for 1 year or greater, bilateral tubal ligation, or hysterectomy. The investigator or designee will also obtain an alopecia history at screening ([Appendix 1](#)). The subject's alopecia history is captured on a separate source document and eCRF and is not documented as part of the subject's general medical history.

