#### 8.1.5. Clinical Laboratory Assessments

A qualified staff member will collect non-fasting samples for clinical laboratory analysis at the visits detailed in Schedule of Assessments (Table 3). Samples will be sent to a central laboratory for analysis. Refer to the study specific laboratory manual for handling and shipping instructions. The following tests will be conducted:

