##### Complete Blood Count

Hematocrit  
Hemoglobin  
Platelet count  
Red blood cell morphology  
Red blood cell count  
White blood cell count  
White blood cell differential  
% & absolute  
Basophils  
Eosinophils  
Lymphocytes

Phosphorus	Monocytes
Potassium	Neutrophils
Sodium	
Total bilirubin	Urinalysis
Total protein	
Uric acid	Screening Only
	Virology (HepB, HCV, HIV)
Total cholesterol, LDL, HDL,	Quantiferon Gold
Triglycerides	Total Iron Binding Capacity (TIBC)
Urine Pregnancy Test for WOCBP (Screening, Baseline, at the visits detailed in Schedule of Assessments (Table 3).	Serum iron
	Serum Ferritin
	T3/ Free T4, TSH
	Serum pregnancy

The following clinical laboratory tests: TIBC, serum iron, serum ferritin, T3/ Free T4, TSH are drawn at screening to rule out any underlying conditions that could be causing alopecia. Total cholesterol, LDL, HDL and Triglycerides will be assessed at all visits. The results of the clinical laboratory tests will be reported on the central laboratory's standard reports. The investigator must note NCS or CS to define the clinical relevance of any result that is outside the normal range for the laboratory. The investigator must date and initial every laboratory report.

The investigator or subinvestigator must review all the Screening (Visit 1) laboratory test results against the study entry criteria and the Study Medication Interruption Criteria [Table 2](#) for each subject prior to Baseline (Visit 2). Subjects with Screening laboratory values meeting the Study Medication Interruption Criteria found in [Table 2](#) must have repeat laboratory testing performed with results meeting the minimum criteria for resumption in order to initiate treatment at Baseline (Visit 2).

The investigator must report all laboratory results that are BOTH outside the normal range for the laboratory AND, in the opinion of the investigator, CS as medical history if found prior to the first study medication treatment or as an AE if found after the first study medication treatment begins. The investigator must review all laboratory reports in a timely manner.

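### Exclusion 11 accepts hepatitis B surface antibody without surface antigen as proof of vaccination, but resolved infection can look the same and core antibody is not addressed

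*Protocol*

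**What the plan says.** Exclusion 11 reads the same in the Protocol synopsis and in Protocol 4.2. It first excludes anyone positive for HIV, hepatitis B or hepatitis C, and does not define a positive hepatitis B result. It then permits vaccinated subjects and describes the evidence for vaccination by two markers only: "Subjects with serologic evidence of Hepatitis B vaccination (HepB surface Ab without the presence of Hep B surface Ag) will be allowed to participate".

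Protocol 8.1.5 gives the screening virology as "Virology (HepB, HCV, HIV", with no hepatitis B components. For the laboratory manual it says: "Refer to the study specific laboratory manual for handling and shipping instructions". It does not send the reader there for the choice of markers. Table 3, footnote 5, fixes the timing: "Hepatitis B and C, TIBC, Serum Iron, Serum Ferritin, T3, free T4, TSH and Serum Pregnancy should be done at screening visit only". The SAP repeats that footnote in its schedule (SAP 1.2) and adds nothing on hepatitis B. Neither document mentions hepatitis B core antibody.

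Several other provisions bear on the point:

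- Exclusion 9 bars "Evidence of active or latent bacterial (including tuberculosis) or viral infections at the time of enrollment".
- Inclusion 8 requires good general health, free of known conditions that would put the subject at unacceptable risk.
- Exclusion 7 covers severe, progressive or uncontrolled hepatic disease, past or present, as judged by the investigator.
- Exclusion 13 covers clinically significant screening laboratory abnormalities.
- Protocol 3.4.1.1 and 3.4.1.2 set ALT/AST thresholds for holding and stopping treatment.

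**The concern.** The exception is meant to let vaccinated people in. The two results it relies on show that surface antibody is present and surface antigen is absent. They do not show how the antibody arose. Someone who cleared a natural infection, perhaps without knowing it, can have the same two results. This is the basic meaning of the tests that the protocol names; the documents do not discuss it.

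The sponsor has chosen to keep hepatitis B positive subjects out of a trial of an oral JAK1/JAK3 inhibitor, a class that Protocol 1.1 describes as able to modulate immune responses. The stated rule may not carry that choice through for past infection. The stake is participant protection at entry.

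There is a smaller consequence for analysis. An unmet entry criterion removes a subject from the per-protocol population (Protocol 9.2, SAP 5.3), so a subject whom the two sentences of Exclusion 11 treat differently could be classed either way. The primary ITT analysis is not affected.

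**Working it through.** The plan states no figure to reproduce. The check is mainly a reading of the rule against the possible serological patterns.

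**Step 1: apply Exclusion 11 to each pattern.**

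| History | Surface antigen | Surface antibody | Core antibody | Result under Exclusion 11 |
|---|---|---|---|---|
| Vaccinated, never infected | negative | positive | negative | exception met |
| Resolved infection, core antibody not tested | negative | positive | unknown | exception met |
| Resolved infection, core antibody tested | negative | positive | positive | exception met on its two markers, but the bar on hepatitis B positive subjects can also be read to apply |

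The first two rows cannot be told apart at the site. In the third row the two sentences of the criterion point in opposite directions, and nothing says which prevails. With about 25 sites (Protocol 3.2), different decisions are possible.

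**Step 2: ask whether another provision identifies the second-row subject before dosing.**

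- Exclusion 9 needs evidence of active or latent infection and names no hepatitis B marker. It may catch a known case.
- Inclusion 8 refers to known disease.
- Exclusion 7 needs a history of, or current, severe, progressive or uncontrolled hepatic disease.
- Exclusion 13, and the repeat testing of screening values that meet Table 2, need an abnormal laboratory result.
- Medical history is limited to conditions that "are ongoing, require concomitant therapy or are, in the opinion of the investigator, relevant" to participation. An unrecognised infection would not be reported.
- The investigator "must review all the Screening (Visit 1) laboratory test results against the study entry criteria", which applies the same criterion.
- The ALT/AST rules on treatment act after dosing has started. They require a hold above 3 x ULN, and permanent discontinuation at 3.4.1.2 levels, such as above 3 x ULN with bilirubin above 2 x ULN or symptoms of liver injury.

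None of these identifies a silent past infection before the first dose.

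**Step 3: illustrate the size.** Inputs from the documents are about 95 subjects and 1:1:1:1 allocation with three active arms (Protocol 3.2 and 3.3). The share p of enrolled subjects who have this pattern from past infection is not in the documents; it is an assumption, shown over a range.

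Active-arm subjects: 95 x 3/4 = 71.25, about 71. Expected number on active drug = 71.25 x p. Chance of at least one, treating subjects as independent = 1 - (1 - p)^71.

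| Assumed p | Expected on active drug | Chance of at least one |
|---|---|---|
| 0 | 0 | 0% |
| 0.5% | 71.25 x 0.005 = 0.36 | 1 - 0.995^71 = 30% |
| 1% | 71.25 x 0.01 = 0.71 | 1 - 0.99^71 = 51% |
| 2% | 71.25 x 0.02 = 1.4 | 1 - 0.98^71 = 76% |

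**The case against.** The best counter-argument is that the panel cannot be seen. The virology entry in 8.1.5 is shorthand: Exclusion 11 itself needs two hepatitis B markers, and 8.1.5 itemises neither. The laboratory manual was not available for this review, and core antibody may well be on the panel. If so, a sensible investigator with a positive core antibody result might decline to call it evidence of vaccination and exclude the subject under the opening sentence. This stands, and it limits the conclusion. A reader might infer that the plan omits core antibody testing, or that it definitely admits people with past hepatitis B. The documents support neither. Even on this reading, though, the criterion does not tell the investigator how to resolve the conflict.

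The second argument is that no harm has been shown. A reader might infer that ATI-501 reactivates hepatitis B. No passage says so, and the statement about immune modulation describes mechanism. That also stands. The case for the change rests on an eligibility rule that does not do what its label says, not on a demonstrated risk.

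Third, the other criteria and the liver rules narrow the practical gap. They do, for known disease and for injury that shows in enzymes, but not for the subject described here.

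Fourth, timing. The current protocol is dated 09APR2019, and the synopsis estimates last completion in July 2019. Counting 24 weeks (168 days) back from 31 July 2019 gives 13 February 2019, so on those estimates randomisation had ended before this version was issued. The documents do not state enrolment status. If the estimates held, the edit would protect few or no subjects in this trial.

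**Conclusion.** The concern holds as a defect in the eligibility wording. Surface antibody without surface antigen does not establish vaccination. Depending on whether core antibody is on the unitemised panel, Exclusion 11 either lets an unrecognised past infection through or leaves sites with contradictory instructions.

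The number affected is unknown and may be zero. The illustration of 0.36 to 1.4 expected active-arm subjects rests wholly on assumed shares of 0.5% to 2%. A reader might apply those shares to all 95 subjects, but the quarter on placebo does not receive the drug, so about 71 is the relevant base.

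The conclusion depends on one piece of general serology that the documents do not state: resolved infection can give the same two results, and core antibody distinguishes it. A reader might also infer that the trial needs HBV DNA monitoring. The documents do not settle whether core-antibody-positive subjects should be admitted under monitoring. That would be a separate and costlier sponsor choice, and it is not part of this point.

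**What to change.** In Exclusion 11, in both the synopsis and Protocol 4.2:

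- Define hepatitis B positive as surface antigen positive or core antibody positive.
- Limit the vaccination exception to subjects who are surface antibody positive with surface antigen and core antibody both negative.

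In Protocol 8.1.5, replace the single hepatitis B entry with the three markers: surface antigen, surface antibody and core antibody.

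The cost is protocol wording, at most one added assay on screening blood already drawn (none if the panel already includes core antibody), and possibly a few more screen failures. No endpoint, planned sample size or analysis method changes.
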